18.9 INSURANCE FOR SUBJECTS

Alfasigma S.p.A will arrange insurance for all study subjects. The following guidelines must be taken into account:

- Any serious adverse event which may be correlated or not to investigational product or diagnostic procedures during the trial must be reported to the sponsor or the CRO immediately.
- The insurance company is entitled to ask all doctors involved in the treatment of a subject, other insurance companies and the national insurance for information which might help to clarify the cause of injury. Before enrolment in the study a subject must be informed of insurance against trial-related injuries and who to contact for compensation.

The terms of the insurance will be included in the Investigator's Study File.

18.10 DISCLOSURE OF ALL INFORMATION AND RESULTS

By signing the protocol, the investigator agrees to keep confidential all information and results concerning the study and the investigational product, until the data are published.

18.11 PUBLICATION POLICY

The Sponsor declare its intent to publish the results of the study, after completion of the regulatory Report.

The personal data especially sensitive data regarding the clinical trial, will be only disseminated in strictly anonymous form.

The Sponsor will work with the protocol development team and will identify a lead author for the manuscript development. The authors for the manuscript will be determined by the amount of effort and participation each Investigator contributes towards the study design, the study conduct, as well as the analysis of study results.

All of the parties agree to provide the other with the text sufficiently in advance to allow examination, prior to submission to a scientific journal.

It is understood by the Investigator that the information developed in the clinical study may be disclosed, as required, to other clinical Investigators, and regulatory authorities.

In the case of a multicenter trial an investigator cannot publish the study results relevant to his/her single center separately, unless global results have already been published.

18.12 OWNERSHIP

All data and records provided by the Sponsor or generated during the study (other than a subject's medical records) and all inventions discovered in the course of conducting the study are the property of the Sponsor. If a written contract for the conduct of the study which includes ownership provisions inconsistent with this statement is executed, then contract's ownership provisions shall apply rather than this statement.

18.13 CONTRACTS, FINANCES

In addition to the protocol trial-related duties, functions and financial aspects must be specified in a

separate contract between Alfasigma S.p.A., the investigator and any other parties involved in the clinical trial.

19 Reporting

After completion of the study an "integrated" full report will be prepared (according to the ICH Harmonized Tripartite Guideline Topic E3 "Structure and Content of Clinical Study Reports").

| | | 
6.3.2.14. Concentration of velusetrag and THRX-830449 metabolite, section 6.4.4 laboratory parameters and section 6.4.6 other safety parameters are updated.
 
Minor changes are applied for Sections related to efficacy endpoint.
 | |
| Draft Version 0.7 | 13-MAR-2023 | 
“Patient” replaced with “Subject”.
 
Start of treatment replaced with pre-treatment.
 
Column “Endpoints” of section 2 updated for safety and tolerability secondary objective.
 
Section 3.3.3 updated included further details to identify prohibited medication.
 
Definition of study phases, Figure 2 and definition of baseline/reference are updated in section 4.2.
 
NOPD03 is included in Table 6.1-1.
 
Details related to the sort of outputs of medical history and prior medication are included in section 6.2. The “abnormal” category of physical examination is splitted in “abnormal CS” and “abnormal NCS” in section 6.2.
 
A listing of [REDACTED] and gastrointestinal symptoms is added in section 6.3.1.
 
Descriptive tables by treatment sequence and period are deleted for primary endpoint (section 6.3.1), [REDACTED]
 
[REDACTED]
 
[REDACTED]
 | Sponsor’s review |

| | |
|---|--|
|  | Statistical Analysis Plan |
| | Sponsor: Alfasigma S.p.A. Protocol: VE-CIP2001/2021 |

| Status and Version | Release Date | Change Description | Reason/Comment |
|--------------------|--------------|---|----------------|
| | |  | |

| | |
|--|--|
| | Statistical Analysis Plan |
| | Sponsor: Alfasigma S.p.A. Protocol: VE-CIP2001/2021 |

| Status and Version | Release Date | Change Description | Reason/Comment |
|--------------------|--------------|---|--------------------|
| | | | |
| Final Version 1.0 | 15-MAR-2023 | First Final Release | Sponsor's approval |
| Draft Version 1.1 | 20-APR-2023 | 
Section 1.1 is updated to report the decision to not considered the variable stratum in the efficacy analyses and all efficacy sections are updated consequently (i.e., 6.3.1, 6.3.2.1, 6.3.2.2, 6.3.2.4, 6.3.2.8).
 
Section 6.1 is updated to better clarify how subject disposition will be described and to drop tables by stratum.
 
Time from CIPO diagnosis date to informed consent signature described in Section 6.2 is computed in years instead of months.
 
The analysis of primary endpoint on FAS is removed in section 6.3.1.
 
Section 6.3.2.9 related to [REDACTED] is updated including additional details.
 
Section 6.3.2.11 [REDACTED] and section 6.3.2.13 [REDACTED] are updated to consider the variables as
 | Sponsor's review |

| | |
|--|---|
| | Statistical Analysis Plan |
| | 
Sponsor: Alfasigma S.p.A.
 
Protocol: VE-CIP2001/2021
 |

| Status and Version | Release Date | Change Description | Reason/Comment |
|----------------------|--------------|--|------------------|
| | | 
categorical and to include data collected for wash-out/follow-up period and statistical model for [REDACTED]. [REDACTED] are removed.
 
Formal adjustment for section 6.4.3.
 
Further details are included for listings with abnormal values in section 6.4.4 and 6.4.6.
 
[REDACTED] are updated in section 6.4.4.
 | |
| Draft Version 1.2 | 09-MAY-2023 | 
Section 1.1 updated with further details on binary outcome and count data. Fisher exact test was included in the section 6.3.2.2 and 6.3.2.13.
 
ATC codes to identify opioids treatments in section 3.3.3 were updated as well as the ATC code to identify patients who took antibiotics in section 6.3.2.7.
 
Including also start date for prior medications (including the [REDACTED] [REDACTED] start date of medical history condition on which imputation rules for partial dates will be applied to compute the study day.
 
Management of [REDACTED] collected with different unit of measurements where there isn't conversion factor applicable to uniform the unit are described for [REDACTED].
 
Similarly, management of [REDACTED] collected as greater than (>) or lower than (<) will be also described.
 
Mixed models for efficacy parameters considered as continuous variables were updated considering the reference of
 | Sponsor's review |

| | |
|--|---|
| | Statistical Analysis Plan |
| | 
Sponsor: Alfasigma S.p.A.
 
Protocol: VE-CIP2001/2021
 |

| Status and Version | Release Date | Change Description | Reason/Comment |
|--------------------|--------------|---|--------------------|
| | | 
Model 2 described in the publication of Chen X, Chen P “A Comparison of Four Methods for the Analysis of N-of-1 Trials” PLoS One. 2014 Feb 4;9(2):e87752. doi: 10.1371/journal.pone.0087752. eCollection 2014. Due to the different approach adopted for continuous variables, the Mixed model planned for binary outcome was removed also due to possible convergence problems.
 
The McNemar Bowker’s test planned for [REDACTED] and [REDACTED] was replaced with Fisher exact test to compare treatment.
 
Formal adjustments.
 | |
| Final Version 2.0 | 10-MAY-2023 | Second Final Release | Sponsor’s approval |

| | |
|--|--|
| | Statistical Analysis Plan |
| | Sponsor: Alfasigma S.p.A. Protocol: VE-CIP2001/2021 |

[figure not shown]
Authorization

The signatures on this page indicate review and approval of the Statistical Analysis Plan, version 2.0, dated May 10, 2023.

[figure not shown]
| | Name | Function | Signature | Date |
|------------------------|------|----------|---|------|
| Author | | | DocuSigned by:  Signer Name:  Signing Reason: I am the author of this document Signing Time: 10-May-2023 18:41 CEST | |
| Reviewer | | | DocuSigned by:  Signer Name:  Signing Reason: I have reviewed this document Signing Time: 10-May-2023 18:46 CEST | |
| Alfasigma S.p.A | | | DocuSigned by:  Signer Name:  Signing Reason: I approve this document Signing Time: 10-May-2023 19:31 CEST | |
| Alfasigma S.p.A | | | DocuSigned by:  Signer Name:  Signing Reason: I approve this document Signing Time: 10-May-2023 23:00 CEST | |

| | |
|---|--|
|  | Statistical Analysis Plan |
| | Sponsor: Alfasigma S.p.A. Protocol: VE-CIP2001/2021 |

TABLE OF CONTENTS

| | |
|---|-----------|
| LIST OF ABBREVIATIONS..... | 11 |
| 1. INTRODUCTION..... | 13 |
| 1.1. CHANGES FROM THE STUDY PROTOCOL..... | 13 |
| 2. STUDY OBJECTIVES AND ENDPOINTS | 14 |
| 3. BACKGROUND AND RATIONALE | 19 |
| 3.1. OVERALL STUDY DESIGN AND PLAN DESCRIPTION | 19 |
| 3.2. SELECTION OF STUDY POPULATION | 21 |
| 3.3. TREATMENT..... | 22 |
| 3.3.1. Treatment Administered..... | 22 |
| 3.3.2. Method of Assigning Subjects to Treatment Group..... | 22 |
| 3.3.3. Prior and Concomitant Therapy | 23 |
| 3.4. SCHEDULE OF TIME AND EVENTS..... | 26 |
| 3.5. SAMPLE SIZE AND POWER ESTIMATION | 29 |

| SS | Safety set |
| T3 | Triiodothyronine |
| T4 | Thyroxine |
|  |  |
| TSH | Thyroid stimulating hormone |
| ULN | Upper Limit of Normal |
| WHO-DD | World Health Organization Drug Dictionary |

[figure not shown]
| | |
|---|--|
|  | Statistical Analysis Plan |
| | Sponsor: Alfasigma S.p.A. Protocol: VE-CIP2001/2021 |

1. INTRODUCTION

This statistical analysis plan (SAP) provides details on the planned statistical analysis for study VE-CIP2001/2021 (CIPO) based on the study protocol final version 1.0 of May 24, 2021.

[figure not shown]
[figure not shown]
1.1. Changes from The Study Protocol

The endpoints "" reported in section 5.2 SECONDARY STUDY OBJECTIVES AND ENDPOINTS of study protocol are analysed 

The Handling of Missing and Incomplete Data for primary endpoint has been modified in case of pre-treatment value missing. 

The reason for this is to reduce data heterogeneity between subjects 

In addition, missing imputation methodology will be applied only for the primary endpoint of the study while all other secondary endpoints will be based on observed data. For this reason, the rules explained in section 16.3.5 Handling of Missing and Incomplete Data of study protocol for the other endpoints are not reported since not applied.

All efficacy analyses, originally planned to be stratified by randomization stratum, will be performed only overall since all patients were randomized to Stratum 2 , except one that was randomized to Stratum 1 

For the binary outcome (Proportion of subjects with 1-point improvement in ), odds ratio and confidence interval using logistic model will be computed while the Cochran-Mantel-Haenszel test will not be performed due to strata distribution and it will be substituted with Fisher Exact test.

| | |
|--|---|
| | Statistical Analysis Plan |
| | 
Sponsor: Alfasigma S.p.A.
 
Protocol: VE-CIP2001/2021
 |

[figure not shown]
Number of [REDACTED] and number of [REDACTED] will be analyzed as categorical variables and will be separately analyzed for treatment and wash-out/follow-up period. [REDACTED]

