This is a phase II, multicenter, double-blind, placebo-controlled, twotreatment four period cross-over, multiple (n=1) trial. Eligible subjects will be treated for 4 periods of 4 weeks each with either velusetrag 15 mg (2 periods) or placebo (2 periods) with a wash-out period of 2 weeks between treatment periods.

After an up to 7-day screening period (from Day -7 to Day -1, V1), at randomization visit (V2), eligible subjects will be randomly allocated to one of the following four sequences:

- A. VEL-PLA-VEL-PLA
- B. PLA-VEL-PLA-VEL
- C. VEL-PLA-PLA-VEL
- D. PLA-VEL-VEL-PLA

Where:

VEL= velusetrag 15 mg once a day for 4 weeks.

PLA= matching placebo once a day for 4 weeks.

There will be a 2-week wash-out period between each treatment period and a final 2-week follow-up period at the end of the last treatment period.

will be registered at Day-1 (referring to the last 7 days including Day-1) and weekly during the study, as appropriate according to the schedule of assessment using a subject's e-diary.

	will be also assessed at screening and
during the study according	to the schedule of assessments. Number
of	will be assessed at each study visit
as well as the	
At the screening visit and	at the end of the first 4-week treatment
period,	will be performed in order to
assess	
Subjects under treatment	t with a
	must have a 5-day
washout period before rand	domization (note: symptomatic treatments
other than	will be permitted through the study, see
below).	

	In case, during a treatment period or during a washout period, a subject should experience an exacerbation of the CIPO related gastrointestinal symptoms that is not controlled by permitted medications and is not judged as an adverse event, he/she will attend an early switch visit (ESV) at the clinical site. After being reassessed, he/she will start the next scheduled treatment period (SOT-2 or SOT-3 or SOT-4) without completing the ongoing treatment or washout period. Only one early switch is possible during the study.
Number of Subjects:	16 (4 subjects per treatment sequence).
Study Population:	Subjects with a diagnosis of idiopathic CIPO or CIPO secondary to primary neurodegenerative or demyelinating conditions (e.g., Parkinsonian Syndromes, multiple sclerosis, etc.).
Inclusion Criteria:	Men or women aged 18-80 years.

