In case, during a treatment period or during a washout period, a subject should experience an exacerbation of the CIPO related gastrointestinal symptoms that is not controlled by permitted medications and is not judged as an adverse event, he/she will attend an early switch visit (ESV) at the clinical site. After being reassessed, he/she will be offered to directly switch to the next scheduled treatment period (SOT-2 or SOT-3 or SOT-4) without completing the ongoing treatment or washout period. Only one early switch is possible during the study. ESV will be Day 1 of the relevant period (SOT-2 or SOT-3) based on the timing of early switch.

In case of ESV/SOT-2 or ESV/SOT-3 or ESV/SOT-4, the subsequent visits will follow the relevant sequential number (see Study Schedule of Assessments).

will be registered on Day-1 (taking into consideration the symptoms relevant to the last 7 days including Day-1) and weekly after randomization, during both treatment and wash out periods, as appropriate according to the Study Schedule of Assessments using a subject's e-diary, until End of Follow-up or in case of ETV or ESV.

[figure not shown]
In addition, investigational product intake and time will be registered by the subjects in the e-diary during the treatment periods daily.

will be also assessed at screening and then, after randomization during the study according to "Study Schedule of Assessments".

At the screening visit and at the end of the first 4-week treatment period, will be performed in order to assess

In order to assess in all subjects on Visit 2 (Day 1) and Visit 3 (Day 28 ± 1), blood samples for assessment of plasma velusetrag and THRX 830449 (metabolite) concentrations will be collected.

Figure 1: Schematic study design

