16.3.2 Secondary Efficacy Endpoints and Statistical Model of Analysis

Continuous efficacy endpoints will be summarized and analyzed in the same way as the primary endpoint. In case of deviation from normality, non-parametric method will be considered. Binary outcome will be compared between treatments with an odds ratio and confidence interval using logistic model and Cochran-Mantel-Haenszel test. Poisson modelling will be used for count data. Full details will be provided in the SAP.

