Subjects under treatment with a 
 must have a 5-day wash-out period before randomization (note: symptomatic treatments other than  will be permitted throughout the study, see section 10.8 Prior and Concomitant Therapy in the study protocol).

If, during a treatment period or during a wash-out period, a subject should experience an exacerbation of CIPO related gastrointestinal symptoms that is not controlled by permitted medications and is not judged as an adverse event, he/she will attend an early switch visit (ESV) at the clinical site. After being reassessed, he/she will be offered to directly switch to the next scheduled treatment period (SOT-2 or SOT-3 or SOT-4) without completing the ongoing treatment or wash-out period. Only one early switch is possible during the study. ESV will be Day 1 of the relevant period (SOT-2 or SOT-3 or SOT-4) based on the timing of early switch.

In case of ESV/SOT-2 or ESV/SOT-3 or ESV/SOT-4, the subsequent visits will follow the relevant sequential number (see Study Schedule of Assessments in section 3.4).

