These flags will be reviewed and updated by means of Medical Review to evaluate if the computed flags are clinically consistent.

[figure not shown]
[figure not shown]
[figure not shown]
- 
- 

[figure not shown]
| | |
|---|--|
|  | Statistical Analysis Plan |
| | Sponsor: Alfasigma S.p.A. Protocol: VE-CIP2001/2021 |

[figure not shown]
- 
- 
- 
- 
- 
- 
- 
- 
- 
- 

[figure not shown]
The numerator will be considered as follows:

- Proportion of days with dose increased (at least 1 medication): 

- Proportion of days with dose increased (1-2 medications): 

- Proportion of days with dose increased (≥ 3 medications): 

- Proportion of days with dose decreased (at least 1 medication): 

[figure not shown]
- Proportion of days with dose decreased (1-2 medications): 

- Proportion of days with dose decreased (≥ 3 medications): 

- Proportion of days with drug added (at least 1 medication): 

- Proportion of days with drug removed (at least 1 medication): 

Analysis methodology

| | |
|---|--|
|  | Statistical Analysis Plan |
| | Sponsor: Alfasigma S.p.A. Protocol: VE-CIP2001/2021 |

[figure not shown]
[figure not shown]
[figure not shown]
[figure not shown]

Data handling rules

No missing imputation will be performed.

[figure not shown]
Definition

The  is a  used to assess generic  outcomes from the subject's perspective. It is often used as a  measure. Generic subject-reported outcome (PRO) measures like the  including the impact of any and all illnesses on a broad range of functional domains. The  consists of a subset of  from the  covering the same  domains of , including 

 (norm based score) that represents  and  components of  and  will be derived by means of the 

Analysis methodology

Data handling rules

No missing imputation will be performed.

6.3.2.11. 

Definition

The number of  during each treatment period will be collected and analyzed as well as the number of  during each wash-out/follow-up period.

| | |
|--|---|
| | Statistical Analysis Plan |
| | 
Sponsor: Alfasigma S.p.A.
 
Protocol: VE-CIP2001/2021
 |

Analysis methodology

[Redacted]

[Redacted]

Data handling rules

No missing imputation will be performed.

[Redacted]

[Redacted]

Definition

The [Redacted] is used to provide an evaluation of the type of diet followed by the subject. [Redacted]

[Redacted]:

| | | |
|------------|------------|------------|
| [Redacted] | [Redacted] | [Redacted] |

Analysis methodology

[Redacted]

[Redacted]

| | |
|---|--|

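### Two count endpoints are analysed as categories of the raw number per period, with no visible allowance for periods that an early switch cuts short

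*SAP*

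**What the plan says.** Protocol Section 16.3.2 sets the method for secondary counts: "Poisson modelling will be used for count data". It names no offset or exposure term and leaves the detail to the SAP.

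SAP Section 1.1 departs from this. Two endpoints, each a number of something blacked out, "will be analyzed as categorical variables and will be separately analyzed for treatment and wash-out/follow-up period". The text directly after that sentence is also blacked out.

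The definitions are in SAP 6.3.2.11 and in a second subsection that the SAP's version log numbers 6.3.2.13. Both say that the number of events "during each treatment period will be collected and analyzed as well as the number of" events in each wash-out or follow-up period. Neither shows a denominator. Their data-handling paragraphs are readable and say only that nothing is imputed. Their analysis-methodology blocks are blacked out. The version log, used here only as support, adds "Fisher exact test was included in the section 6.3.2.2 and 6.3.2.13", and for two blacked-out endpoints records that an earlier test "was replaced with Fisher exact test to compare treatment".

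On early switching, SAP Section 3.1 moves the subject to the next treatment period "without completing the ongoing treatment or wash-out period". Protocol Section 6 gives the trigger: an "exacerbation of the CIPO related gastrointestinal symptoms that is not controlled by permitted medications and is not judged as an adverse event". The protocol synopsis allows one switch per subject, and protocol Section 11.2.8 places it between Day 1 and Day 126. The switch visit is itself Day 1 of the next period, with dosing that day.

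**The concern.** A count only means something against the time over which it was collected. A completed treatment period lasts 4 weeks and a completed wash-out 2 weeks. A treatment period ended by a switch is shorter, and no wash-out follows it; a switch during wash-out shortens the wash-out. If all of these are classified by their raw number, a subject observed for half a period is compared on equal terms with one observed for all of it.

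The lost time is not random. A switch happens because symptoms are uncontrolled, so if one treatment controls symptoms less well, more of its time is lost. Its raw counts then tend to come out too low, which narrows the difference between treatments. This would work against velusetrag if placebo periods are cut more often, and would soften an unfavourable result if velusetrag periods are.

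The SAP already anticipates the problem elsewhere. Section 4.2 adjusts first and last intake dates for a switch, Section 6.4.1 derives exposure in weeks per treatment period, and the medication-change endpoint is expressed as a proportion of days. Nothing visible carries that through to the two counts.

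**Working it through.** **The plan's own figures.** None is given for these endpoints. The only computed design figures are the power table for the primary endpoint. It reproduces (18 pairs, effect size 0.7: 79.9% against the stated 80%) but has no bearing here.

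**Inputs from the documents.** 16 subjects with 2 placebo periods each give 16 × 2 = 32 placebo periods. One switch per subject caps the switched share at 16/32 = 50%. Period 4 and the follow-up cannot be cut by a switch, although early termination can shorten them.

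**Assumptions, because the documents give no switch or event rates.** All switches fall on placebo; a switched period is observed for a fraction *f* of its length; *k* switches give a share *s* = *k*/32; events occur at a constant rate.

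**1. Equal true rates, mid-period switches (*f* = 0.5).** Remaining placebo time is E = 1 − *s*(1 − *f*), and the apparent velusetrag/placebo count ratio is 1/E.

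| Switches | Remaining time E | Apparent velusetrag/placebo ratio |
|---|---|---|
| 4 | (32 − 2)/32 = 94% | 1.07 |
| 6 | (32 − 3)/32 = 91% | 1.10 |
| 8 | (32 − 4)/32 = 88% | 1.14 |

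**2. The same effect in categories.** Take a Poisson rate of 1 event per full period in both arms and 8 switches at mid-period. The proportion of periods with at least one event is 1 − exp(−1) = 63.2% on velusetrag. On placebo it is 0.75 × 63.2% + 0.25 × (1 − exp(−0.5)) = 57.2%. Putting counts into categories does not remove the shortfall.

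**3. A real placebo excess.** Suppose the true placebo/velusetrag rate ratio is 1.5. The raw ratio is 1.5 × E:
- 4 switches at mid-period: 1.41
- 8 at mid-period: 1.31
- 16 (the ceiling) at mid-period: 1.5 × 0.75 = 1.12
- 16 at one quarter of the period: 1.5 × 0.625 = 0.94

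Dividing by observed time returns 1.5 in every row. The arms change order only if the true ratio is below 1/E, that is 1.07, 1.14, 1.33 and 1.60 in these four rows.

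**4. Higher rate in the switched periods.** Let 8 placebo periods switched at mid-period carry twice the ordinary rate. The full-period ratio would be 0.75 + 0.25 × 2 = 1.25. The raw ratio is 0.75 + 0.25 × 2 × 0.5 = 1.00. Events per observed time give 1.00/0.875 = 1.14. The rate analysis recovers part of the difference, not all of it.

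**5. The triggering exacerbation counted as an event.** Add one event to each switched period, with equal background rates. For 8 mid-period switches and a background of 1 per period, the placebo mean is 0.75 × 1 + 0.25 × (0.5 + 1) = 1.125, so placebo shows more events, not fewer. Over 8 or 16 switches, *f* of 0.25 or 0.5 and background rates of 0.25 to 1, the placebo/velusetrag ratio runs from 1.06 to 2.75.

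**The case against.** The strongest objection is the blackout. The places where a rate, an exposure term or a restriction to completed periods would be written are unreadable for both endpoints. A reader might infer that the plan makes no allowance; the documents support only that none is visible. What remains is that the readable parts, including the data-handling paragraphs, contain no rule for shortened periods.

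A reader might also infer that both endpoints are formally tested. The version log ties Fisher's exact test by number to 6.3.2.13 only, so 6.3.2.11 may be descriptive. The fix is therefore conditional on a treatment comparison being made.

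The illustration puts every switch on placebo yet keeps event rates equal, and 8 switches means half the subjects. That is fair criticism: it isolates the effect of lost time and is not a forecast.

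For wash-outs, one could score a wash-out that never happened as zero events and obtain larger distortions. SAP Section 1.1 bases secondary endpoints on observed data, which points to treating it as no observation. No wash-out figure is claimed here.

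The SAP tabulates switches and discontinuations by period (Section 6.1) and derives exposure (Section 6.4.1), so unequal time would not be invisible. That helps interpretation but does not correct the comparison.

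Finally, the protocol's Poisson model states no offset, so the SAP removed no visible exposure adjustment, and restoring that model unchanged would not solve the problem.

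**Conclusion.** The concern holds in a limited form. The visible text analyses the number of events per period as categories, outcome-related switches shorten some periods, and no adjustment for observed time can be seen. Under a constant rate, raw counts understate events on the treatment that loses more time. With 4 to 8 mid-period switches, all on placebo, the apparent velusetrag/placebo ratio at equal true rates is 1.07 to 1.14.

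It is tempting to conclude that the treatment with more failures will show fewer events. The documents do not support that. The general result is a smaller apparent difference; reversal needs many or very early switches with a modest true difference. Because the endpoint names are blacked out, one cannot tell whether the triggering exacerbation is itself counted, in which case the direction can be the opposite.

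The reach is restricted by the cap of one switch per subject and the Day 126 limit. These are secondary endpoints, and the primary analysis is unaffected.

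**What to change.** In SAP Sections 1.1, 6.3.2.11 and 6.3.2.13:

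- For any treatment comparison of these endpoints, analyse events per observed day with a Poisson model that has log(days observed in the period) as offset and a subject effect. If events are too sparse to fit it, compare events per observed time within subjects with an exact test, for example a sign-flip test on each subject's velusetrag-minus-placebo difference.
- State that a wash-out that did not occur is not observed, and is not scored as zero events.
- State whether the exacerbation that triggers a switch counts as an event. Item 5 of the working shows that this decides the direction.
- Tabulate observed days by treatment and period type, and keep the category table as description.

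If the blacked-out text already contains such rules, it is enough to confirm them.

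The cost is SAP wording and simple programming: observed days follow from intake, switch-visit and scheduled-visit dates already collected. The drawback is wide intervals if events are sparse. An offset also does not fully correct for switched periods having a higher event rate (item 4), so the table of observed days should be read alongside the estimate.
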